#### 4.8.1 AE date imputation

Date imputation is the creation of a new, complete date from a partial one according to an agreed and acceptable algorithm. Missing date for AE will be handled according to rules specified below. A partial date is simply an incomplete date e.g. DD OCT 2001: the days are missing from this DDMMYYYY date.

Partial AE start dates, if left partial, would ultimately mean the following

It would not be possible to place the AE in time.

Therefore the treatment/dosage at the time of the event would be unknown.

Therefore the event could not be reported/summarized appropriately - if at all.

Therefore it is important to perform date imputation to ensure that as many data events are represented as completely as possible. Of course partial and/or missing dates should *also* be caught as edit checks and passed back to the investigator for resolution.

There **will be no** attempt to impute the following:

- **Missing** AE start dates
- AE start dates **missing the year**

- Partial/missing AE end dates

The following [Table 4-4](#) explains the abbreviations used.

**Table 4-4 AE/treatment date abbreviations**

	Day	Month	Year
Partial Adverse Event Start Date	<not used>	AEM	AEY
Treatment Start Date TRTSTD	<not used>	TRTM	TRTY

The following matrix [Table 4-5](#) describes the possible combinations and their associated imputations. In the light grey boxes the upper text indicates the imputation and the lower text the relationship of the AE start date to the treatment start date (TRTSTD).

#### 4.8.2 Incomplete date of initial diagnosis of cancer, date of most recent recurrence and date of anti-neoplastic therapies

Missing day is defaulted to the 15th of the month and missing month and day is defaulted to 01-Jan.

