### 2.7.3 Handling of missing values/censoring/discontinuations

Confirmed PR or CR reported prior to any additional anticancer therapy will be considered as responses in the calculation of the ORR in respect of the number of missed assessments before response.

Patients with a best overall response (BOR) of 'Unknown' or 'Not Assessed per RECIST 1.1' will be considered as non-responders when estimating ORR.

Patients who have disease progression and continue to receive study drug after progression will qualify for PD at the time of progression and will be counted as PD in the derivation of ORR and any other efficacy endpoints.

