## Best overall response

The BOR will be assessed based on reported lesion responses at different evaluation time points. Both CR and PR require confirmation at least 4 weeks after its initial observation.

Only tumor assessments performed before the start of any further anti-neoplastic therapies (i.e. any additional secondary anti-neoplastic therapy or anti-cancer surgery) will be considered in the assessment of BOR. If a patient receives any further anti-neoplastic therapy while on study, any subsequent assessments will be excluded from the BOR determination. Further anti-neoplastic therapies will be identified via protocol deviations or from the data collected on 'Anti-neoplastic therapies since last date of study drug' as appropriate. Clinical deterioration will not be considered as documented disease progression. Patients with BOR 'unknown' will be summarized by reason for having unknown status. The following reasons will be used:

- No valid post-baseline assessment
- All post-baseline assessments have overall response UNK
- New anti-neoplastic therapy started before first post-baseline assessment
- Stable disease (SD) too early ( $\leq 6$  weeks after start date of study drug)
- PD too late ( $> 12$  weeks after start date of study drug)

Special (and rare) cases where BOR is 'unknown' due to both early SD and late PD will be classified as 'SD too early'.

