## Progression-free survival

PFS is defined as the time from the start date of study drug to the date of the first radiologically documented PD or death due to any cause.

If a patient has not progressed or is not known to have died at the date of analysis cut-off or has received any further anticancer therapy, PFS will be censored at the date of the last adequate tumor evaluation before the cut-off date or before the start of the new anticancer therapy date, whichever is earlier. Clinical deterioration will not be considered as a qualifying event for progression. Refer to [Table 2-1](#) for censoring and event date options and outcomes for PFS.

In particular, PFS will be censored at the last adequate tumor assessment: **if** one of the following occurs: absence of event; the event occurred after a new anticancer therapy is given; the event occurred after two or more missing tumor assessments (see [Section 4.6.1](#)). See also [Section 4.6.1](#) describing the special case of a missing baseline tumor assessment.

PFS will be described in tabular and graphical format using Kaplan-Meier methods as described for DOR, including estimated median (in months) with 95% CI, 25th and 75th percentiles and Kaplan-Meier estimated probabilities with corresponding 95% CIs at several time points (including at least 4, 8, 12, 15 and 18 months). Censoring reasons will also be summarized.

These analyses will be performed separately based on investigator assessment and based on BIRC assessment.

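### SAP 4.8.2 completes partial anticancer-therapy dates with no lower bound, so new therapy can be dated on or before progression (and, for year-only dates, before a confirmed response)

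*SAP*

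**What the plan says.** The imputation rule in SAP 4.8.2 is one unconditional sentence: "Missing day is defaulted to the 15th of the month and missing month and day is defaulted to 01-Jan". The heading covers the date of initial diagnosis, "date of most recent recurrence and date of anti-neoplastic therapies". It does not say prior therapies, and no bound is given at first dose, last dose or progression.

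The start of further therapy is then used in these places:

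- **ORR (SAP 2.7.3).** "Confirmed PR or CR reported prior to any additional anticancer therapy will be considered as responses".
- **Best overall response (SAP 2.8.1).** "Only tumor assessments performed before the start of any further anti-neoplastic therapies" are used, and "If a patient receives any further anti-neoplastic therapy while on study, any subsequent assessments will be excluded from the BOR determination". One listed reason for an unknown best response is "New anti-neoplastic therapy started before first post-baseline assessment". Under SAP 2.7.3 an unknown best response counts as non-response.
- **PFS (SAP 2.8.1).** Censoring is at the last adequate evaluation before the cut-off "or before the start of the new anticancer therapy date, whichever is earlier". One listed ground for censoring is that "the event occurred after a new anticancer therapy is given".
- **DOR and PFS (SAP Table 2-1, row F).** A patient given new anticancer therapy is censored at the last adequate assessment.

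Neighbouring date rules are anchored. In SAP 4.8.4 a partial death date is the later of last contact and the default date. In SAP 4.8.1 an adverse event whose order relative to treatment start is uncertain is generally moved to the day after treatment start (Table 4-7).

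**The concern.** Protocol 6.3.2.1 bars other anticancer therapy during treatment, and Protocol 7.1.4.1 captures later therapy on an eCRF page for the time after the last dose. A date from that page that is imputed to before the last dose therefore contradicts recorded data. New therapy often follows progression closely, so a small backward shift can reverse the order of the two. A true PFS or DOR event then becomes a censoring at the previous scan. A large backward shift can also remove the scans that established a response.

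Partial dates are foreseeable. Later therapies are collected by contact every 3 months (Protocol 7.1.5.2), without clinic visits (Protocol 4.1). The SAP as shown plans no PFS or DOR analysis that disregards new therapy, so a reversed order would not show up in the results.

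**Working it through.** **The plan's own figures.** The design passes with at least 17/43 and then at least 45/105 responses. P(stop) = P(Bin(43, p) ≤ 16). P(success) = Σ over x = 17 to 43 of P(Bin(43, p) = x) × P(Bin(62, p) ≥ 45 − x). At p = 0.35 these give 0.6828 and 0.0487; at p = 0.50 they give 0.0631 and 0.9000. They match Protocol Table 10-1 and SAP Table 2-3 (0.683 and 0.049; 0.063 and 0.900). The imputation rule does not enter this calculation.

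**Day missing, therapy g days after PD.** The default date falls on or before PD only if PD is on the 15th or later and therapy starts in the same month. In a month of L days that leaves L − g − 14 PD dates (zero if negative). An ordinary year has seven months of 31 days, four of 30 and one of 28. The last column leaves out ties, where PD is itself on the 15th (L − g − 15 dates).

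| g (days) | PD dates affected per year | Share of 365 | Share without ties |
|---|---|---|---|
| 1 | 7×16 + 4×15 + 13 = 185 | 51% | 173/365 = 47% |
| 7 | 7×10 + 4×9 + 7 = 113 | 31% | 101/365 = 28% |
| 10 | 7×7 + 4×6 + 4 = 77 | 21% | 65/365 = 18% |
| 14 | 7×3 + 4×2 + 0 = 29 | 8% | 18/365 = 5% |
| 16 | 7×1 = 7 | 2% | 0 |
| 17 or more | 0 | 0% | 0 |

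A day-by-day enumeration over 2014–2017 gives the same shares. PD dates are taken as evenly spread over the calendar. Ties matter because the response rule keeps only scans before therapy, while the PFS wording speaks of events after it.

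Example: PD on 20 October, therapy on 28 October recorded as October. The default is 15 October, so PD falls after new therapy and PFS is censored at the previous scan. On the 8-week schedule that is about 25 August.

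**Day missing, effect on response.** The largest backward shift is 31 − 15 = 16 days. For therapy after PD, the default date is therefore never more than 15 days before PD. It cannot reach a confirmation scan 28 or more days before PD (0% in the enumeration). A response can be lost this way only if therapy starts within 16 days of the confirming scan, for example without prior PD.

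**Day missing, the opposite error.** Therapy g days before PD is dated after PD when PD falls on days g + 1 to 14 of the same month, which is 14 − g dates. For g = 1: 12 × 13/365 = 43%. For g = 7: 12 × 7/365 = 23%. For g = 14: 0%. A PD that should be censored is then counted as an event.

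**Day and month missing.** The backward shift is up to 364 days (365 in a leap year). The date falls on or before PD whenever PD and therapy share a calendar year, a share of (365 − g)/365:

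- g = 7: 358/365 = 98%
- g = 28: 337/365 = 92%
- g = 90: 275/365 = 75%

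For a response confirmed 168 days before PD (an assumption), the date also falls on or before the confirmation scan in (365 − g − 168)/365 of cases:

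- g = 7: 190/365 = 52%
- g = 28: 169/365 = 46%
- g = 90: 107/365 = 29%

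If the first dose was given after 1 January of the same year, the date precedes treatment. Every post-baseline scan is then excluded.

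**Size per patient.** 124 patients were treated (Protocol, Amendment 4 rationale), which is the FAS by definition. One lost response moves ORR by 1/124 = 0.81 points.

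**The case against.** **Scope.** The heading lists therapies beside diagnosis and recurrence, which are baseline history, so the rule may be meant for prior therapy only. That reading is plausible. However, SAP 2.3 writes prior when it means prior, and on this reading the SAP as shown has no rule for partial dates of later therapy. A sentence is needed either way. The body of Protocol Appendix II is not shown and could hold a rule, although SAP 4.8.2 does not refer to it.

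**Response loss.** A reader might infer that the 15th rule routinely deletes responses. It does not. For therapy after PD the shift is too short, and loss comes in practice only from year-only dates.

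**Direction.** A reader might infer that PFS and DOR are always lengthened. Turning prompt post-PD therapy into censoring works that way, but the 15th rule can also create events, so a net direction is not established.

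**The 45-of-105 decision.** A reader might infer that the trial's success rule is at risk. SAP 1 states that this plan is for the final analysis. The decision belongs to the earlier primary analysis, whose date rules are not shown. SAP 2.7.2 repeats the test, so the final ORR could move, but no effect on the decision is demonstrated.

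**Frequency.** The documents give no count of partial therapy dates, and the total effect may be small. This stands.

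**Conclusion.** The point holds in limited form. Followed as written, SAP 4.8.2 can place therapy given after study drug on or before PD, and a year-only date can also fall before the confirming scan or the first dose. The main exposure is PFS and DOR event status. With the day missing it is confined to gaps of at most 16 days within one month (15 if ties are not counted). ORR is exposed in practice only through year-only dates, at 0.8 points per lost response.

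The percentages are conditional on a partial date and a given gap. They are not the share of trial patients affected, which is unknown. They assume PD dates spread evenly over the year, and the response figures also assume confirmation 168 days before PD. The Simon design's alpha and power are unaffected.

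**What to change.** Change SAP 4.8.2 as follows:

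1. Limit the present rule to diagnosis, recurrence and prior-therapy dates.
2. For therapies recorded after study drug, use the later of the present default and the day after the last dose, kept within the recorded month and year.
3. Respect any documented order relative to PD. The last-dose bound gives 0% reversals for every gap tested (1 to 90 days) only when the last dose is on or after PD. If drug stopped on 1 October, PD was on 20 October and therapy is recorded as October, the bound gives the later of 2 and 15 October, which is still before PD.
4. For therapies during treatment, which SAP 2.8.1 identifies through protocol deviations, bound the date below by the first dose.
5. Flag imputed therapy dates in the listings.

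The cost is one or two SAP sentences and a small programming change. No new data are needed.

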#### 4.8.3 Incomplete assessment dates for tumor assessment

All investigation dates (e.g. X-ray, CT scan) must be completed with day, month and year.

If one or more investigation dates are incomplete but other investigation dates are available, the incomplete date(s) are not considered for calculation of the assessment date and assessment date is calculated as the latest of all investigation dates (e.g. X-ray, CT-scan) if the

overall lesion response at that assessment is CR/PR/SD/UNK. Otherwise, if overall lesion response is PD, the assessment date is calculated as the earliest date of *all* investigation dates at that evaluation number. If all measurement dates have no day recorded, the 1st of the month is used.

[figure not shown]
If the month is not completed, for any of the investigations, the respective assessment will be considered to be at the date which is exactly between the previous and the following assessment. If both a previous and following assessments are not available, this assessment will not be used for any calculations.

#### **4.8.4 Incomplete date for death**

All dates must be completed with day, month and year.

If the day or month is missing, death will be imputed to the maximum of the last contact date (excluding the date of death) and the following:

- Missing day: 1st day of the month and year of death
- Missing day and month: July 1st of the year of death

